1. VERSION HISTORY

This Statistical Analysis Plan (SAP) for study B7461009 is based on the Protocol dated 25 June 2018.

| Table 1. | Summary of Major Changes in SAP Amendments |
|----------|--|
|----------|--|

| SAP Version | Change | Rationale |
|-------------|----------------|----------------|
| 1 | Not Applicable | Not Applicable |

2. INTRODUCTION

This SAP provides the detailed methodology for summary and statistical analyses of the data collected in study B7461009. This document may modify the plans outlined in the protocol; however, any major modifications of the primary endpoint definition or its analysis will also be reflected in a protocol amendment. This analysis plan is meant to supplement the study protocol. Any deviations from this analysis plan will be described in the Clinical Study Report.

2.1. Study Objectives

Primary:

• To evaluate the effect of hepatic impairment on the steady state pharmacokinetics of lorlatinib.

Secondary:

- To evaluate the effect of hepatic impairment on the safety of lorlatinib in advanced cancer patients.
- To evaluate the antitumor activity of lorlatinib in advanced cancer patients.

CCI

2.2. Study Design

This will be a Phase 1, open-label, multi-center, multiple-dose, non-randomized, Phase 1 clinical trial of lorlatinib in advanced cancer patients with varying degrees of hepatic impairment and necessary age-, weight-, and gender-matched prospect normal hepatic function patients.

Patients in the study will be assigned to different groups according to their liver function. The criteria for stratification of patients based on their liver function (according to National Cancer Institute (NCI) guidance,¹ *https://ctep.cancer.gov/protocolDevelopment/docs/CTEP_Organ_Dysfunction_Protocol_Te mplate.docx) are listed below:*

| Group | Groups A1 | Group B | Group C | Group D |
|-----------|-------------------|-------------------------|--------------|------------|
| | and A2 | | | |
| Hepatic | Normal | Mild impairment | Moderate | Severe |
| Function | | _ | impairment | impairment |
| Total | \leq ULN (Upper | $B1: \leq ULN$ | >1.5 x - 3 x | >3 x ULN |
| Bilirubin | Limit of | B2: > 1.0 x - 1.5 x ULN | ULN | |
| | Normal) | | | |
| AST | $\leq ULN$ | B1: > ULN | Any | Any |
| (SGOT) | | B2: Any | - | |

- Patients must fulfill both total bilirubin and AST (serum glutamic oxaloacetic transaminase [SGOT]) criteria to be included in a group.
- No distinction will be made between liver dysfunction due to metastases or liver dysfunction due to other causes.
- All liver function tests for stratification must be completed within 24 hours prior to the start of treatment.
- Group B (Mild hepatic impairment): for the purpose of this study, the "mild" liver dysfunction may be defined according to either of two criteria (Groups B₁ and B₂), so that patients in Group B may come from either of these groups. Patients in Group B₁ and B₂ are thus considered to have comparable liver dysfunction and will be combined for dose level allocation and all analysis.
- Patients whose degree of hepatic dysfunction changes (becomes worse or better) between screening and initiation of protocol therapy may be re-assigned to a different hepatic dysfunction group. This change should be discussed with the Sponsor and properly documented. Patient stratification will only be done prior to initiation of the study treatment. Patients will not be re-assigned to a different hepatic dysfunction group once treatment with lorlatinib has been started.
- Groups A1 and A2 (Normal): patients with normal liver function will be included in this study as matching control patients (Group A1 for Group B and Group A2 for Group C). If the dose for moderate hepatic impairment group (Group C) is selected to be the recommended clinical dose of 100 mg QD, the control group A2 will not be needed to be enrolled. There will be no control group designated to match severe group. However, if a decision has been made to use the same dose for severe and moderate patients, the half of the control Group A2 will be matching Group C and half will be matching Group D.

The enrollment of approximately 76 advanced cancer patients is anticipated in this study in order to have 8 PK-evaluable patients in each of Groups A1, A2, B and C, and 6 PK-evaluable patients in Group D for final statistical analysis. Evaluable patients are those who complete the planned PK sample collection on Cycle 2 Day 1 and have no lorlatinib dose modification until completion of Cycle 2 Day 1 PK evaluation. Patients who are not evaluable for PK will be replaced.

Each patient will be treated with repeated oral once daily doses of lorlatinib in 21-day cycles until disease progression, patient refusal, or unacceptable toxicity occurs.

The planned dosing schedule for each treatment group is as follows:

| | Group B | Group C | Group D | Group A1 | Group A2 |
|-----------------|-----------|--------------|-------------|-----------|----------|
| Hepatic | Mild | Moderate | Severe | Normal | Normal |
| Function | | | | | |
| Starting | 100 mg QD | 50 mg QD or | determined | 100 mg QD | the same |
| Lorlatinib Dose | | otherwise | based on | | dose as |
| | | determined | preliminary | | Group C |
| | | in the first | safety and | | at the |
| | | stage | PK data | | second |
| | | | | | stage |
| Lorlatinib Dose | 100 mg QD | 50 mg QD or | determined | 100 mg QD | 100 mg |
| After PK | | otherwise | based on | | QD |
| Assessment | | determined | preliminary | | |
| | | in the first | safety and | | |
| | | stage | PK data | | |

Table 2. Lorlatinib Dosing Schedule

The dose schedule may be modified as necessary for individual patients according to tolerability (see Table 2 for detailed dose modification strategy).

For Group C, a two-stage enrollment will be applied.

- In the first stage, 3 PK-evaluable patients will be enrolled to receive the starting dose of 50 mg QD lorlatinib. On completion of PK sample collection through Cycle 2 Day 1 from these 3 patients, PK analysis will be performed. Upon review of the PK and tolerability of these 3 patients, a decision on dose schedule for remaining patients in the second stage will be made.
- *In the second stage:*
 - If it is decided to keep the planned dosing schedule (50 mg QD) for patients in Group C with moderately impaired liver function, 5 additional patients will be enrolled to have a total of 8 PK evaluable patients.

• If a different dosing schedule is proposed for the remaining patients in Group C based on safety and PK in the first 3 subjects, then more patients will be enrolled to this group to have 8 PK evaluable patients and receive the proposed dosing schedule. The control patients in Group A2 should receive the same lorlatinib dose as proposed for the second stage in Group C until completion of PK assessment on Cycle 2 Day 1 and then switch to 100 mg QD beyond Cycle 2 Day 1. At the new dose level, the first 3 patients should be dosed one at a time with at least one week apart until some safety information at this dose level is obtained.

The enrollment for patients with severe hepatic impairment (Group D) will only be started when the dose for patients in the second stage of Group C has been determined and has been tolerated in at least one patient. The initial lorlatinib dose for Group D might be the same as the second stage Group C dose or otherwise determined by sponsor based on available preliminary safety and PK data at that time. The dosing regimen for Group D will be communicated to sites. Patients in Group D will not be matched by any control group. Initially (the first 3 patients), the patients should be dosed one by one with at least 1 week apart until some safety information is obtained at the dose level.

Patients in Groups A1 (Normal hepatic function) and B (Mild hepatic impairment) will receive a starting lorlatinib dose of 100 mg (4×25 -mg tablets) QD. The first 3 patients in in Group C (Moderate hepatic impairment) will receive a starting lorlatinib dose of 50 mg (2×25 -mg tablets) QD. Patients in control Group A2 (Normal hepatic function) will receive the same starting lorlatinib dose as stage 2 of Group C, which could be 50 mg (2×25 -mg tablets) QD or as otherwise determined during the second stage of Group C, and switch to 100 mg (4×25 -mg tablets) QD after completion of PK assessment on Cycle 2 Day 1.

Enrollment into control Group A2 will only be started after the first stage for Group C has been completed and a decision on dose schedule for the stage 2 subjects in Group C has been made. Patients in control group should match patients in the respective hepatic impaired group by the following criteria:

- The mean body weight in control group will be within ±20 kg of the mean body weight of the patients in respective hepatic impaired group.
- The mean age in control group will be within ± 10 years the mean age of the patients in respective hepatic impaired group.
- The gender ratio in control group will be similar (±2 patients per gender) to those in respective hepatic impaired group.

Once all the patients complete their planned PK collection, data collection for the primary objective of the study will be accomplished. After data collection for the primary objective has been completed, the sponsor could generate a study report including all PK data and other data, as defined in the Sponsor-maintained statistical analysis plan. In this case, a supplement study reported will then be generated when all patients completed the study.

3. ENDPOINTS AND BASELINE VARIABLES: DEFINITIONS AND CONVENTIONS

3.1. Primary Endpoint(s)

Plasma PK parameters of lorlatinib at steady state: AUC₂₄ and C_{max}.

3.2. Secondary Endpoint(s)

- Type, incidence, severity, seriousness, and relationship to study medications of adverse events (AE) and any laboratory abnormalities.
- Objective response rate (ORR).
- Duration of response (DR).
- Plasma PK parameters of lorlatinib, if possible: AUC_{last}, T_{last}, and T_{max} after single dose; C_{min}, AUC_{last}, T_{last}, and CL/F at steady-state.
- Plasma PK parameters for metabolite(s) if possible: AUC₂₄, AUC_{last}, C_{max}, T_{max}, T_{last} MRAUC₂₄, MRAUC_{last}, and MRC_{max}

3.3. Baseline Variables

The date of first dose (start date) of study treatment is the earliest date of non-zero dosing of the study drug. The date of last dose of study treatment is the latest date of non-zero dosing of the study drug.

No windowing will be applied when defining baseline. Any deviations from the protocol specified window will be documented as protocol deviations.

For efficacy analyses the last assessment prior to randomization will serve as the baseline assessment.

For safety (including Eastern Cooperative Oncology Group (ECOG) performance status) the last assessment performed on or prior to date of the first dose of study treatment will serve as the baseline assessment. If there are no observations meeting these criteria, then baseline is considered missing.

Triplicate ECGs are collected; therefore the baseline for each ECG measurement is the average of the pre-dose measurements on the baseline day. Unscheduled assessments will not be included in the calculation of the average.

3.4. Analysis Sets

Data for all subjects will be assessed to determine if subjects meet the criteria for inclusion in each analysis population prior to releasing the database and classifications will be documented per standard operating procedures.

3.4.1. Full Analysis Set

The full analysis set includes all enrolled patients, regardless of whether or not treatment was received.

3.4.2. PK analysis sets

3.4.2.1. PK Concentration Analysis Set

The PK concentration analysis set is defined as all enrolled patients who are treated and have at least 1 analyte concentration.

3.4.2.2. PK Parameter Analysis Set

The PK parameter analysis set is defined as all enrolled patients treated who have sufficient information to estimate at least 1 of the PK parameters of interest.

3.4.2.3. PK evaluable Analysis set

The PK evaluable analysis set is defined as all patients in the PK parameter analysis population who have (1) completed Cycle 2 Day 1 PK collection; (2) received lorlatinib dose on Cycle 2 day 1; (3) received at least 80% of total dose within 14 days prior to Cycle 2 Day 1; (4) no dose reduction in the first cycle.

3.4.3. Safety Analysis Set

The safety analysis (SA) population will include all enrolled patients who receive at least one dose of lorlatinib on Cycle 1, Day 1. The safety analysis population will be the primary population for evaluating patient characteristics, treatment administration, and safety.

3.4.4. Response Evaluable Analysis Set

The response evaluable analysis set includes all patients in the safety analysis population who have an adequate baseline tumor assessment.

4. GENERAL METHODOLOGY AND CONVENTIONS

Once all the patients complete their planned PK collection, data collection for the primary objective of the study will be accomplished. After data collection for the primary objective has been completed, the sponsor could generate a study report including all PK data and other data.

4.1. Hypotheses and Decision Rules

The study is not powered to detect treatment difference in PK parameters. No formal statistical hypothesis testing is planned, and no decisions will be made to the conduct of the study.

The sample size for this study is determined empirically based on feasibility and regulatory recommendation. Sufficient numbers of patients will be enrolled and dosed to obtain approximately 38 PK evaluable subjects (approximately 16 subjects in normal group, 8 patients each in mild and moderate groups, and 6 in severe group). Subjects may be replaced if not PK evaluable.

4.2. General Methods

4.2.1. Analyses for Binary Data

The point estimates of the rate will be provided along with the corresponding exact 2-sided 95% confidence intervals using the exact Clopper-Pearson method based on the F-distribution.²

4.2.2. Analyses for Continuous Data

For continuous variables, summaries will include N, Mean, S.D., CV%, 25th quartile, median, and 75th quartile, min and max. One-way analysis of variance (ANOVA) will be used to test for difference between treatment groups.

4.2.3. Analyses for Categorical Data

The number and percentage of patients in each category will be provided for categorical variables.

4.2.4. Analyses for Time to Event Data

Time-to-event endpoint will be summarized using the Kaplan-Meier method³ and displayed graphically when appropriate. Median event times and 2-sided 95% confidence interval for each median will be provided (Brookmeyer R and Crowley JJ).⁴

4.3. Methods to Manage Missing Data

In compliance with Pfizer standards, if the day of the month is missing for any date used in a calculation, the 1st of the month will be used to replace the missing date unless the calculation results in a negative time duration (eg, date of resolution cannot be prior to date of onset; if replacing resolution date with the 1st of the month results in a negative duration, the resolution date will be set to the onset date.). In this case, the date resulting in 0 time duration will be used. Pfizer standards are also used if both month and day are missing (Jan 1 unless negative time duration).

For the analysis of safety endpoints, the Pfizer data standard rules for imputation will be applied.

4.3.1. Pharmacokinetic Concentrations

4.3.1.1. Concentrations Below the Limit of Quantification

In all data presentations (except listings), concentrations below the limit of quantification (BLQ) will be set to zero. (In listings BLQ values will be reported as "<LLQ", where LLQ will be replaced with the value for the lower limit of quantification.)

4.3.1.2. Deviations, Missing Concentrations and Anomalous Values

In summary tables and plots of median profiles, statistics will be calculated having set concentrations to missing if 1 of the following cases is true:

1. A concentration has been collected as ND (ie not done) or NS (ie no sample),

2. A deviation in sampling time is of sufficient concern or a concentration has been flagged anomalous by the pharmacokineticist.

Note that summary statistics will not be presented at a particular time point if more than 50% of the data are missing.

4.3.2. Pharmacokinetic Parameters

Actual PK sampling times will be used in the derivation of PK parameters.

If a PK parameter cannot be derived from a subject's concentration data, the parameter will be coded as NC (ie, not calculated). (Note that NC values will not be generated beyond the day that a subject discontinues).

In summary tables, statistics will be calculated by setting NC values to missing; and statistics will not be presented for a particular treatment if more than 50% of the data are NC. For statistical analyses (ie, analysis of variance), PK parameters coded as NC will also be set to missing.

If an individual subject has a known biased estimate of a PK parameter (due for example to an unexpected event such as vomiting before all the drug is absorbed in the body), this will be footnoted in summary tables and will not be included in the calculation of summary statistics or statistical analyses.

4.3.3. Efficacy Endpoints

For duration of response (DR), if calculation based on conventions result in a negative value, durations will be reset to 1 day.

For efficacy analyses no values will be imputed for missing data, except as specified in Section 5.2.2, where for time to event endpoint DR, non-event observations will be censored, and for ORR, patients with no post-baseline tumor evaluations will be counted as non-responders.

4.3.4. ECG Parameters

For analyses of ECG parameters, no values will be imputed for missing data. If one or two of the triplicate measurements for an ECG parameter are missing, the average of the remaining two measurements or the single measurement can be used in the analyses. If all triplicate measurements are missing at a time point for an ECG parameter, no values will be imputed for this time point and no analyses related to this time point will be performed.

5. ANALYSES AND SUMMARIES

All summaries will be provided by hepatic function group. Patients treated on different dose levels within the same hepatic function group will be categorized by dose level (eg, Group C split into Group C1 and C2).

5.1. Primary Endpoint(s)

5.1.1. Pharmacokinetic Analysis

5.1.1.1. Pharmacokinetic Parameter Analysis Methods

Pharmacokinetic parameters will be derived from the lorlatinib and its metabolite(s) concentration-time profile as described in Table 3.

| Table 3. | Pharmacokinetic Parameter Derivation |
|----------|--------------------------------------|
|----------|--------------------------------------|

| Parameter | Definition | Method of Determination |
|-----------------------|---|--|
| AUC _{last} | Area under the plasma | linear-log trapezoidal method |
| | concentration-time profile from | |
| | time zero to the time of the last | |
| | quantifiable concentration | |
| | (C_{last}) | |
| AUC_{24} | Area under the plasma | linear-log trapezoidal method |
| | concentration-time profile | |
| | during one dosing interval | |
| | (24 hours) | |
| C_{max} | Maximum plasma concentration | Observed directly from data |
| C_{min} | Minimum plasma concentration | Observed directly from data |
| T_{max} | Time for C_{max} | Observed directly from data as time of |
| | | first occurrence |
| CL/F | Apparent clearance | $Dose/AUC_{24}$ at steady-state |
| MRAUC _{last} | Metabolite ratio for AUC _{last} | (AUC _{last} /MW) _{metabolite} /(AUC _{last} /MW) _{lorlatinib} |
| $MRAUC_{24}$ | Metabolite ratio for AUC ₂₄ | (AUC ₂₄ /MW) _{metabolite} /(AUC24/MW) _{lorlatinib} |
| MRC _{max} | Metabolite ratio for C_{max} | $(C_{max}/MW)_{metabolite} / (C_{max}/MW)_{lorlatinib}$ |

MW= molecular weight; F= oral bioavailiability

Actual PK sampling times will be used in the derivation of PK parameters. In the case that actual PK sampling times are not available, nominal PK sampling times will be used in the derivation of PK parameters.

The effect of the hepatic impairment on PK parameters will be assessed by constructing 90% confidence intervals around the estimated difference between each of the Test and the Reference using a one-way ANOVA model based on natural log transformed data.

One-way analysis of variance (ANOVA) will be used to compare the natural log transformed AUC_{24} , AUC_{last} and C_{max} of lorlatinib at steady state for each of the hepatic impairment groups (Test) to the corresponding normal hepatic function group with the same dosing schedule (Reference). Group B (Test) will be compared to Group A1 (Reference) and Group C (Test) will be compared with Group A2 (Reference). If a decision has been made to use the same dose for severe and moderate patients, the half of the control Group A2 will be matching Group C and half will be matching Group D (test), and the corresponding pairwise comparisons will be made. Additionally, Group D will be compared to Group A1 (Reference), and Group C will be compared with A1. Estimates of the mean differences (Test-Reference) and corresponding 90% confidence intervals will be obtained from the

model. The mean differences and 90% confidence intervals for the differences will be exponentiated to provide estimates of the ratio of geometric means (Test/Reference) and 90% confidence intervals for the ratios.

Residuals from the models will be examined for normality and the presence of outliers via visual inspection of plots of residuals vs predicted values and normal probability plots of residuals but these will not be included in the clinical study report. If there are major deviations from normality or outliers then the effect of these on the conclusions will be investigated through alternative transformations and/or analyses excluding outliers. Justification for any alternative to the planned analysis will be given in the report of the study.

The following PK parameters will be summarized descriptively by analyte, hepatic function group and at C1D1 and C2D1 for lorlatinib and its metabolites.

| Parameter | Summary statistics |
|--|--|
| AUC _{24,} AUC _{last} , C _{max} , C _{min} , CL/F, MRAUC _{24,} MRAUC _{last} , MRC _{max} | N, arithmetic mean, median, cv%, standard deviation, minimum, maximum, geometric mean. |
| T _{max} | N, median, minimum, maximum. |

Box and whisker plots for individual subject parameters (lorlatinib AUC $_{24}$, AUC_{last} and C_{max}) will be presented against hepatic function group by analyte and overlaid with geometric means.

PK parameter analysis set will be used for performing the analysis.

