- Groups A1 and A2 (Normal): patients with normal liver function will be included in this study as matching control patients (Group A1 for Group B and Group A2 for Group C). If the dose for moderate hepatic impairment group (Group C) is selected to be the recommended clinical dose of 100 mg QD, the control group A2 will not be needed to be enrolled. There will be no control group designated to match severe group. However, if a decision has been made to use the same dose for severe and moderate patients, the half of the control Group A2 will be matching Group C and half will be matching Group D.

Child-Pugh scores (criteria listed in Appendix 3) will be calculated and recorded as part of the liver function testing prior to the start of the first lorlatinib dose, but will not be used to stratify patients into treatment groups.

The enrollment of approximately 76 advanced cancer patients is anticipated in this study in order to have 8 PK-evaluable patients in each of Groups A1, A2, B and C, and 6 PK-evaluable patients in Group D for final statistical analysis. Evaluable patients are those who complete the planned PK sample collection on Cycle 2 Day 1 and have no lorlatinib dose modification until completion of Cycle 2 Day 1 PK evaluation. Patients who are not evaluable for PK will be replaced.

Each patient will be treated with repeated oral once daily doses of lorlatinib in 21-day cycles until disease progression, patient refusal, or unacceptable toxicity occurs.

The planned dosing schedule for each treatment group is as follows (Table 4):

	Group B	Group C	Group D	Group A1	Group A2
Hepatic Function	Mild	Moderate	Severe	Normal	Normal
Starting Lorlatinib Dose	100 mg QD	50 mg QD or otherwise determined in the first stage	determined based on preliminary safety and PK data	100 mg QD	the same dose as Group C at the second stage
Lorlatinib Dose After PK Assessment	100 mg QD	50 mg QD or otherwise determined in the first stage	determined based on preliminary safety and PK data	100 mg QD	100 mg QD

Table 4.Lorlatinib Dosing Schedule

The dose schedule may be modified as necessary for individual patients according to tolerability (see Table 6 for detailed dose modification strategy).

For Group C, a two-stage enrollment will be applied.

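### If Groups C and D share a dose other than 100 mg QD, halving control Group A2 leaves about 4 same-dose controls per comparison instead of 8 and widens the log-scale 90% CIs by about 22-23% (C) and 20% (D).

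*SAP*

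**What the plan says.** SAP 5.1.1.1 compares log-transformed AUC24, AUClast and Cmax at steady state for each impaired group "to the corresponding normal hepatic function group with the same dosing schedule (Reference"). Group B is compared with A1 and Group C with A2. For the case where C and D receive the same dose, it adds that "the half of the control Group A2 will be matching Group C and half will be matching Group D (test"). The same sentence then ties this allocation to the analysis: "and the corresponding pairwise comparisons will be made". The next sentence reads: "Additionally, Group D will be compared to Group A1 (Reference), and Group C will be compared with A1". The section closes with: "PK parameter analysis set will be used for performing the analysis".

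Protocol 3.1 and SAP 2.2 carry the same split ("the half of the control Group A2 will be matching Group C and half will be matching Group D"). Both also say that if Group C's dose is 100 mg QD, "the control group A2 will not be needed to be enrolled". The targets are "8 PK-evaluable patients in each of Groups A1, A2, B and C", plus 6 in Group D. Later in the same two sections, D is said to be matched by no control group, without the same-dose exception.

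The example code in SAP Appendix 2 covers A1, A2, B and C only. SAP 4.1 states that the study is not powered and that no formal hypothesis test is planned.

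**The concern.** The ratios of geometric means for AUC24 and Cmax, with their 90% confidence intervals, are the primary result. When C and D share a dose, every A2 patient is a same-dose normal control for both. Dividing them discards half of the available reference information from each comparison.

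None of the usual reasons for a split applies:

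- The ANOVA is unpaired, so using a control twice breaks no pairing.
- No joint test is planned, so shared controls create no multiplicity problem.
- The SAP already uses A1 as Reference for B, C and D.

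Neither document gives a reason for the split, the resulting reference n, or a rule for placing an A2 patient in one half or the other. In an open-label study, that last gap leaves the denominator of a primary ratio open to choice after data are seen. The two comparisons would also rest on two different estimates of normal exposure at one dose.

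The added contrasts against A1 do not make up the loss. In this branch A1 is on 100 mg QD while C and D are not, and no dose normalisation is stated. Protocol 1.2.1.2.1.1 reports that auto-induction seems more prominent at higher doses, so a cross-dose ratio mixes dose with hepatic function.

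**Working it through.** **Plan's own figure.** Targets from Protocol 3.1: A1 = A2 = B = C = 8 and D = 6. Total 4 × 8 + 6 = 38, of which 8 + 8 = 16 are normal. This agrees with Protocol 9.2 and SAP 4.1. The documents state no interval width for any comparison.

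**Reference n under the split.** 8 / 2 = 4 for C and 4 for D.

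**Formula.** Log-scale 90% half-width = t(0.95, df) × s × √(1/n_test + 1/n_ref). The residual SD s cancels in the ratio of split to whole.

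**Single model with A1, A2, B, C, D.** df = 38 − 5 = 33 with A2 whole, and 38 − 6 = 32 if A2 becomes two levels.

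| Comparison | n | SE factor | t | Half-width / s |
|---|---|---|---|---|
| C, whole A2 | 8 vs 8 | √(1/8+1/8) = 0.500 | 1.6924 | 0.846 |
| C, half A2 | 8 vs 4 | √(1/8+1/4) = 0.612 | 1.6939 | 1.037 |
| D, whole A2 | 6 vs 8 | √(1/6+1/8) = 0.540 | 1.6924 | 0.914 |
| D, half A2 | 6 vs 4 | √(1/6+1/4) = 0.645 | 1.6939 | 1.093 |

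Half-width ratios: C 1.226, D 1.196. The SE ratios alone are 1.225 and 1.195.

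**Other model choices.**
- Other half left out of the five-group model (df 33 to 29): C 1.230, D 1.200.
- Four-group model of Appendix 2, other half left out (df 28 to 24): C 1.232.
- Separate two-group models, which the SAP does not describe: C 1.260 (df 14 to 10), D 1.247 (df 12 to 8).

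**Larger groups.** The analysis uses the PK parameter set, so numbers may exceed the targets. With all groups 1.5 or 2 times larger (2 × 38 = 76, the anticipated enrolment), the ratios are 1.225 and 1.196.

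**On the ratio scale.** For an observed ratio of 1 and log SD = √ln(1 + CV²), single model, df 33 to 32:

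| CV and source (Protocol Tables 2 and 3) | C, whole to half | D, whole to half |
|---|---|---|
| AUC 39% (50 mg QD, n=3; also 100 mg QD Phase 2, n=26), log SD 0.376 | 0.73-1.37 to 0.68-1.48 | 0.71-1.41 to 0.66-1.51 |
| AUC 53% (75 mg QD, n=12), log SD 0.498 | 0.66-1.52 to 0.60-1.68 | 0.63-1.58 to 0.58-1.72 |
| Cmax 27% (50 mg QD, n=3), log SD 0.265 | 0.80-1.25 to 0.76-1.32 | 0.78-1.27 to 0.75-1.34 |
| Cmax 48% (75 mg QD, n=12), log SD 0.455 | 0.68-1.47 to 0.62-1.60 | 0.66-1.52 to 0.61-1.65 |

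**Cost of equal precision with dedicated halves.** 2 × 8 = 16 A2 patients instead of 8.

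**Price of sharing A2.** Correlation of the two log ratios = (1/8) / √[(1/8+1/8)(1/6+1/8)] = 0.46.

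**Matching on gender.** Read the tolerance of 2 per gender as patient counts. Against a Group C of 8, a half of 4 can meet it with one gender split only, and with none if C has fewer than 2 of either gender. A whole A2 of 8 has 3 to 5 admissible splits. Over all 9 × 7 = 63 gender make-ups of C and D, unweighted, one whole A2 can satisfy both groups in 43; two halves can each satisfy their own in 35.

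**The case against.** The strongest reply is that matching here means demographic matching. Protocol 3.1 and SAP 2.2 use the word for group means of weight and age and for gender ratio, and the split sentence first appears among the recruitment text. SAP 5.1.1.1 also says without condition that C is compared with A2, and Appendix 2 keeps A2 as one level. This reading is possible. But in SAP 5.1.1.1 the split leads directly into the comparisons to be made, so about 4 controls each is the natural reading. The appendix is only an example and omits D. If the demographic reading is intended, the text still needs to say that all of A2 is the Reference.

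Second, no sample-size statement promises 6 vs 8 for D; by default D has no designated control. That is true. The 6 vs 8 baseline follows from the SAP's own same-dose definition of the Reference, so the 20% for D is measured against that definition, while the 8 vs 8 for C is a documented target.

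Third, dedicated controls can be chosen to resemble each impaired group more closely. This is a real trade-off, but the tolerances are wide and apply to group means. The gender count gives no sign that halving helps, although it is weak evidence: it weights every make-up equally and reads a ratio criterion as counts.

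Fourth, the branch is conditional, the study is unpowered, and no decision threshold depends on interval width. That stands, and it limits the seriousness of the point.

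**Conclusion.** The concern holds. If C and D share a dose other than 100 mg QD, the plan as naturally read gives each about 4 same-dose controls where 8 qualify. The log-scale 90% intervals for the primary ratios are then about 22-23% wider for C and 20% wider for D. This assumes the PK-evaluable targets, a pooled-variance single ANOVA, and that matching governs the comparison as well as recruitment. The percentages do not depend on the assumed CV and hardly change if all groups grow together; separate two-group models would make them larger (26% and 25%). The consequence is lost precision and an undefined assignment of controls. It is not a bias or a wrong decision rule. Since using all of A2 for both groups costs no patients, the plan should be changed.

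**What to change.** In Protocol 3.1 and SAP 2.2 and 5.1.1.1, replace the split with wording such as: *If Groups C and D receive the same dose and Group A2 is enrolled, all Group A2 patients in the PK parameter analysis set serve as Reference for both Group C and Group D.*

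In addition:

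- Check the age, weight and gender tolerances for the whole of A2 against C and against D, and report any tolerance not met beside the affected ratio.
- Add Group D to the Appendix 2 model (level order A1, A2, B, C, D) with the D vs A2 contrast 0 -1 0 0 1, and extend the existing contrasts with a zero for D.
- Add the same-dose exception to the sentences in Protocol 3.1 and SAP 2.2 that say D has no control group.

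If the sponsor keeps the split, state the reason, the reference n for each comparison, and how each A2 patient is assigned to a half.

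The cost is text only: edits in Protocol 3.1, SAP 2.2, SAP 5.1.1.1 and SAP Appendix 2. A protocol amendment may be needed if the change counts as a major modification of the primary analysis under Protocol 9 and SAP 2. The downsides are two ratios that share a reference (correlation about 0.46), which matters little without a joint test, and possibly a looser demographic fit for one of the two groups.
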